5 STUDY POPULATION

5.1 INCLUSION CRITERIA

Inclusion criteria for Aims 1 and 3

In order to be eligible to participate in this study, an individual must meet all of the following criteria:

1. Provision of signed and dated informed consent form
2. Stated willingness to comply with all study procedures and availability for the duration of the study
3. Male or female, aged 45 – 80 years
4. Able to read and speak English or Spanish

Inclusion criteria for Aim 2

Two Aim 2 practices are selected by each of their 5 affiliated PBRNs based upon willingness to participate and variability of primary care practice type within the PBRN. Differences in practice size, staffing, ownership, prior quality improvement engagement, geography, patient population socioeconomic status (SES) or languages spoken are among the among the selection criteria the PBRNs will utilize to choose.

Clinician participants (10 practices with up to 15 clinicians per practice):

1. Provision of signed and dated informed consent form.
2. Stated willingness to comply with availability and all study procedures for the duration of aim 2 by the 10 practices (through PBRN recruitment) and their up to 15 clinicians within (through informed consent).

Patient participants [200 patients (approximately 40 from each PBRN)] for CAPTURE survey:

1. Provision of signed and dated informed consent form.
2. Stated willingness to comply with all study procedures and availability for the duration of the study.
3. Male or female, aged 45 – 80 years.

5.2 EXCLUSION CRITERIA

Exclusion criteria for Aims 1 and 3

An individual who meets any of the following criteria will be excluded from participation in this study:

1. Previous clinician provided diagnosis of COPD
2. Treated respiratory infection (with antibiotics and/or systemic steroids) in the past 30 days of baseline
3. Participants unable to perform spirometry due to any of the following conditions within the past 30 days of baseline
 - a) Chest surgery
 - b) Abdominal surgery
 - c) Eye surgery
 - d) Heart attack
 - e) Stroke

Exclusion criteria for Aim 2

1. Clinician participants: current employment at practices participating in aims 1 and/or 3
2. Clinician participants: from practices providing fewer than 2 clinician participants
3. Patient participants: meeting the exclusion criteria for aims 1 and 3 (above)

5.3 SCREEN FAILURES

PBRN coordinators, in conjunction with clinical study site personnel, will pre-screen individuals who are unlikely to be able to complete research spirometry. These individuals will be considered *pre-screen failures*.

Participants who are consented to participate but have a prior clinician diagnosis of COPD will be considered *screen failures*.

5.4 STRATEGIES FOR RECRUITMENT AND RETENTION

Recruitment and retention strategies for Aims 1 and 3

Approximately 4800 participants will be recruited from 100 primary care clinics affiliated with six PBRNs. Each PBRN has centrally-based research coordinators with a history of success working in PBRN practices, documented expertise in previous large diagnostic or therapeutic trials, and personnel experienced in recruitment and data collection.

IRB approval will be obtained at each PBRN for approval for patient contact, informed consent and participation in this study.

All patients who meet all inclusion and no exclusion criteria at the participating PBRN clinical site will be eligible for participation. Research coordinators will work with participating practices to identify and approach potential participants. Recruitment strategies may vary depending on the practice.

Enrollment of participants will depend on the gender, ethnic and racial makeup of those that are being recruited from the practices included in this trial. No exclusion criteria apply specifically to women or to minorities. The Data Coordinating Center (DCC) will track enrollment of participants throughout the course of this study. If women and minorities are under-represented in the initial phase of recruitment, a commitment exists to develop recruitment strategies that target these populations so the final study group is a well-balanced representation of the studied population.

Recruitment and retention strategies for Aim 2

Clinician participants: Approximately 150 clinic participants are recruited by: 1) introductory telephone contact with the practice leadership by PBRN research coordinators and the aim 2 research team; 2) follow up letter, time commitment infographic and informed consent forms sent to interested practices outlining aim 2 clinician participant activities and responsibilities; and 3) in-person aim 2 study explanation to clinician participants at the committed practices during the introductory baseline study site visit.

Clinician participant recruitment draws from both prescribing (or “provider”) staff and non-prescribing (or “clinical support”) staff. The aim 2 research team will attempt to obtain an even mix of both clinician staff types from each practice. Retention incentive of clinician participants over 2 years includes provision of on-line COPD education to all clinician participants and monetary incentive to practices as determined by each individual PBRN.

Patient participants: 200 participants (40 from each PBRN) are recruited as a sub-set of the aim 1. Each NIH-FDA Clinical Trial Protocol Template – v1.0 7 Apr 2017

of the 200 patient participants in aim 2 are asked to complete a one-time 10-minute written opinion survey. Their aim 2 participation is concluded at the end of the opinion survey completion.

The aim 2 research team and DCC will track enrollment and retention of all aim 2 participants throughout the course of the 2-year aim 2 study.

6 STUDY INTERVENTION

6.1 STUDY INTERVENTION(S) ADMINISTRATION

6.1.1 STUDY INTERVENTION DESCRIPTION

The study intervention is applicable to Aims 2 and 3 and consists of healthcare provider education modules.

The practitioners at the 10 sites selected for Aim 2 will receive module 1, Basic COPD education, and may elect to take modules 3-5 for supplemental information on COPD.

For Aim 3, half of the practices will receive Basic COPD education (module 1) and half will receive Basic COPD Education and CAPTURE Education (modules 1 and 2). Practitioners at practices randomized to COPD only education must take module 1 and may elect to take modules 3-5; however, they will not take module 2. Practitioners at practices randomized to COPD+CAPTURE education must take modules 1 and 2, and may elect to take modules 3-5.

1 - Basic COPD Education will be provided in order for providers to optimally manage patients with COPD. The education will incorporate evidence-based recommendations using the 2018 update of the Global Obstructive Lung Disease Strategy(45). For practices enrolled in the pandemic and post pandemic periods, additional information will be provided regarding COPD management in the pandemic era as well as information on steps to maintain patient and staff safety in the clinical sites where CAPTURE patients will be enrolled and assessed.

A 40-minute overview will be presented in the most expeditious manner at each practice site, for example by webinar for all practice personnel over the lunch hour, or audiovisual presentation available on a dedicated CAPTURE web site. The PBRNs have indicated that this module should be no longer than 40 minutes. Topics will include: CAPTURE study description and rationale, importance of COPD in the region of the local practices, COPD definition and diagnosis, patient goals, and management approach. Attendance at this mandatory training will be documented and continuing education credits will be provided for physicians and nurse practitioners by National Jewish Health, an accredited CME provider.

2 - CAPTURE education. An online audiovisual module will be developed to explain CAPTURE interpretation and use in patient evaluation and diagnosis of COPD. This module will only be available to practices randomized to receive the results of CAPTURE for clinical use.

With the information provided in Aim 2 about practice preferences for education, the CAPTURE education module will be revised and made available to practices enrolled in Aim 1 after the completion of Aim 2.

3 - Online advanced COPD education will be available for all practices and continuing education credits will be provided to enhance practitioner participation. Practitioner attendance at each online audiovisual module will be collected including the amount of time spent on each education module, completion of each module with a post-test and evaluation, and CME will be provided. Education will be case-based and will include role playing where appropriate. Seven basic modules of 20 minutes or less will be available both to practices randomized to receive CAPTURE results for clinician use and to control practices that will not receive CAPTURE results and will cover:

1. Diagnosis of COPD: How to diagnose COPD in primary care including medical history, physical exam and role of spirometry, severity categorization
2. Spirometry overview: Basic clinical interpretation
3. Advanced spirometry: Test performance, evaluating quality, advanced case-based interpretation
4. Management overview: Patient goals, smoking cessation, vaccination, patient education, shared decision-making
5. Pharmacotherapy: Inhaled bronchodilators, inhaled corticosteroids
6. Other therapies: Oxygen, pulmonary rehabilitation, surgical approaches
7. Inhalation devices: Patient education

4 – On-site COPD education. Additional funds will be sought to provide on-site COPD education. We have experience in successfully providing half-day on-site education to primary care practices to enhance their management of COPD.

5 – Social media and case conferences. We will use social media (Facebook and Twitter) to provide ongoing education about COPD. Facebook and Twitter posts will provide tips on managing COPD. Online conferences will be scheduled to discuss cases submitted by primary care providers.

6.2 MEASURES TO MINIMIZE BIAS: RANDOMIZATION AND BLINDING

For Aims 1 and 3, this study will use randomization and blinding as two of the cardinal principles of clinical trials to minimize bias.

Randomization. Practices will be randomized into one of the two interventions, COPD education or COPD education + CAPTURE education, in a 1:1 manner, stratified by PBRN. Randomization will occur at the time of site activation and each site will be assigned a unique randomization number. The DCC will prepare the randomization schedule, using computer-generated block randomization with the block size(s) known only by the DCC. A secure web-based application will be built that will be used by the central study coordinators to enter site information (e.g., site ID, stratification factor) and to obtain the randomization number. The information can be printed and sent and/or emailed directly to the study coordinator.

Blinding. This is a single-blind study with the participants blinded to whether their practitioners have received CAPTURE education and patient-level CAPTURE results. Practitioners at sites that are randomized to the control arm (COPD education alone) will be blinded to the CAPTURE questionnaire and PEF results. All practitioners and participants will be blinded to the baseline COPD status of the participants (i.e., blinded to spirometry results), except for safety reasons. In this situation, participants and their clinician will be notified if a participant's post-bronchodilator FEV₁ is less than 30% predicted. For all other participants, they and their practitioners will be blinded to research spirometry results. The coordinator should make every effort to conceal the spirometry results from the participants in these latter cases. Study coordinators should also make every effort to conceal the administration of a post-bronchodilator spirometry test from the practice staff so as not to unblind the physicians to abnormal spirometry.

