2.3 RISK/BENEFIT ASSESSMENT

2.3.1 KNOWN POTENTIAL RISKS

Potential risks associated with Aims 1 and 3 of this study are outlined below.

Spirometry: Participants may become short of breath. Syncope, light-headedness and fainting may develop during this test. These are uncommon.

Albuterol: Tremulousness, feeling of a strong, rapid heartbeat, and palpitations can occur with inhaled albuterol. A targeted safety questionnaire will be administered to all participants prior to albuterol to exclude those with a previous adverse event with the medication. Note that albuterol is only administered to those with abnormal spirometry on the baseline spirometry assessment (defined as $FEV_1/FVC < 0.70$ or $FEV_1 < 80\%$ predicted).

Peak Expiratory Flow: Participants may become short of breath. Syncope, light-headedness and fainting may develop during this test. These are uncommon.

Other non-physical risks of the study include those from economic loss from participation in the study; this will be minimized by scheduling tests and evaluations in a timely manner in the fewest number of visits possible. Patient and physician participants will be provided a modest fee to cover their time to participate in the study.

We anticipate few adverse events due to the non-invasive nature of the study procedures and the rarity of such events encountered during the initial visits and longitudinal follow-up. Medical care will be available at each Clinical Center to treat participants who develop adverse events during in-person study visits.

Potential risks associated with Aim 2 of this study include:

No more than minimal risk exists for participants within aim 2.

Confidentiality of information and identification are the risks associated with this project. Based on previous research and the protocols that have been developed, we believe that the likelihood of these risks to the participants would be minimal, i.e. "rare".

Potential risks associated with the study (all Aims) include:

Loss of confidentiality of study data: This is unlikely since data collected will be stored in locked file cabinets in locked rooms at the Clinical Centers. In addition, only participant IDs are used to identify participants in the secure server at the Data Coordinating Center.

Poor quality data: If the data collected are of poor quality such that it is not useable to achieve study aims, participants will have unnecessarily been exposed to other risks in the study.

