A pre-defined subgroup of enrolled participants, who meet any of the below criteria will undergo longitudinal follow-up at 12 months,

- Participants with a CAPTURE Score ≥ 5 or CAPTURE score of 2, 3, or 4 with a low PEF, defined as <350 L/min for males and <250 L/min for females
- Participants who have abnormal spirometry results, defined as post-bronchodilator FEV₁/FVC < 0.7 or FEV₁ $< 80\%$ predicted at baseline. If a participant is unable to complete a post-bronchodilator spirometry (refusal, technical error on the part of coordinator, etc.), and the pre-bronchodilator FEV₁/FVC is less than 0.65 or FEV₁ is less than 70% predicted, the participant will be considered to have abnormal spirometry for the purpose of follow-up in this study.
- A random sample of approximately 5% who do not meet criteria 1 - 2

Participants who meet the criteria for follow-up will be sent notification shortly after enrollment, and receive reminders at 3, 6, and 9 months. Patient-reported data will be collected by COPD Foundation via telephone, secure web-based server, or mail-based methodologies, based on participant preference.

Subject medical data will be collected from the medical record to assess for changes in practice-level care.

The hypothesis for Aim 3 is that sites where COPD and CAPTURE education and patient-level CAPTURE data are provided to clinicians will exhibit improved COPD diagnosis and COPD-related care compared to sites where COPD education is provided to clinicians.

In exploratory analyses to examine the potential impact of SARS CoV-2 infection on the patient symptoms and health care utilization a simple COVID-19 questionnaire, based on other ongoing NHLBI cohort studies, has been introduced.

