Spirometry is a valid, reproducible means of documenting the presence and severity of airflow limitation. When properly performed with maximum effort and attention to the details of calibration of the instrument, spirometry maneuvers are among the most reproducible of biomedical measures. In the setting of a highly trained, experienced therapist, a coefficient of variation of 2-3% is not unusual. Spirometry will be performed in a standardized manner in accordance with the ATS guidelines, as described in the manual of procedures (MOP). Spirometry is the timed-based measurement of the amount of air that can be forcefully exhaled from the lungs after a full inspiration. In the forced expiratory vital capacity maneuver, a person inhales as big a breath as possible and then blows it out as fast and as long as possible until no more air can leave the lungs. The volume of air leaving the lungs is recorded continuously throughout the maneuver in order to allow calculation of important measures of lung function.

NHANES prediction equations, which are programmed into the Easy On PC spirometers, will be used to

calculate the predicted lung function levels. These require the input of age, height, and race/ethnicity (White, Black, Hispanic). For people of mixed or unknown race the White prediction equations will be used.

PBRN Research Coordinators will be trained and certified in the performance of spirometry testing. Spirometry will be sent for central review for quality control assurance.

Adjudication of the Presence of Obstruction on Post-Bronchodilator Spirometry

The presence of obstruction is determined by the presence of an FEV₁/FVC ratio less than 0.70 after the administration of a bronchodilator. A bronchodilator will be administered to study subjects whose baseline FEV₁/FVC is less than 0.70 or whose FEV₁ is less than 80% of the predicted value.

If a subject is unable to complete a post-bronchodilator spirometry (refusal, technical error on the part of coordinator, etc.), and the pre-bronchodilator FEV₁/FVC is less than 0.65, the patient will be considered to have COPD for the purpose of follow-up in this study.

Height and weight

Height and weight will be recorded in order to determine appropriate prediction equations for spirometry and possible effect of obesity on spirometry. Height will be recorded and weight will be measured prior to spirometry testing.

Demographic Data Collection

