8.4.4 ADVERSE EVENT REPORTING

All AEs that occur at baseline visit will be recorded in the case report form and reported to the DCC. We anticipate few adverse events due to the non-invasive nature of the study procedures. Participants will only be enrolled if they meet the study eligibility criteria, including assessment for contraindications for NIH-FDA Clinical Trial Protocol Template – v1.0 7 Apr 2017

spirometry. Targeted safety questions will be asked of all patient participants prior to albuterol to exclude those with a previous adverse event with the medication and others at high risk due to cardiac abnormalities.

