7.3 Randomization and Blinding

Randomization: Practices will be randomized into one of the two interventions, COPD education or COPD education + CAPTURE education, in a 1:1 manner, stratified by PBRN. Randomization will occur at the time of site activation and each site will be assigned a unique randomization number. The DCC will prepare the randomization schedule, using computer-generated block randomization with the block size(s) known only by the DCC. A secure web-based application will be built that will be used by the central study coordinators to enter site information (e.g., site ID, stratification factor) and to obtain the randomization number. The information can be printed and sent and/or emailed directly to the study coordinator.

Blinding: This is a single-blind study with the participants blinded to whether their practitioners have received CAPTURE education and patient-level CAPTURE results. Practitioners at sites that are randomized to the control arm (COPD education alone) will be blinded to the CAPTURE questionnaire and PEF results. All practitioners and participants will be blinded to the baseline COPD status of the participants (i.e., blinded to spirometry results), except for safety reasons. In this situation, participants and their clinician will be notified if a participant's post-bronchodilator FEV₁ is less than 30% predicted. For all other

participants, they and their practitioners will be blinded to research spirometry results. The coordinator should make every effort to conceal the spirometry results from the participants in these latter cases. Study coordinators should also make every effort to conceal the administration of a post- bronchodilator spirometry test from the practice staff so as not to unblind the physicians to abnormal spirometry.

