7.6 Baseline Assessments and Data Collection

CAPTURE Questionnaire: Participants will complete the five-item self-administered questionnaire. The questionnaire will be scored on a scale of 0-6, with higher scores indicating a higher likelihood of COPD diagnosis. The score calculated and recorded by study site personnel will be used in all primary analyses, regardless of whether the score agrees with the individual CAPTURE questionnaire responses, since the study site personnel's CAPTURE scoring represents the information conveyed to clinical providers.

Peak Expiratory Flow (PEF): PEF will be measured for all participants in L/min, with a quality assurance range of 100-1000 L/min. The participant will perform three PEF tests. All three measurements will be recorded, and the largest of the measurements will be used in the CAPTURE Tool. The study site personnel's indication on the scored CAPTURE form about whether the maximum PEF falls below the predetermined threshold of <350L/min (males) or <250L/min (females) will be used to define CAPTURE+ participants in all primary analyses, regardless of whether that indication agrees with the individually recorded PEF values.

Spirometry: Spirometry will be performed for measurement of forced vital capacity (FVC), forced expiratory volume in one-second (FEV₁), and calculation of FEV₁/FVC. FEV₁ and FVC are measured in liters and have expected ranges of 0.4-8.0 liters. FEV₁ values less than 30% of the predicted values will be adjudicated by the study chair.

NHANES prediction equations, which are programmed into the Easy On PC spirometers, will be used to calculate the predicted lung function levels. These require the input of age, height, race, and sex. For people of mixed or unknown race the White prediction equations will be used.

Adjudication of the Presence of Obstruction on Post-Bronchodilator Spirometry: The presence of obstruction is determined by the presence of an FEV₁/FVC ratio less than 0.70 after the administration of a bronchodilator. A bronchodilator will be administered to study subjects whose baseline FEV₁/FVC is less than 0.70 or whose FEV₁ is less than 80% of the predicted value.

If a subject is unable to complete a post-bronchodilator spirometry (refusal, technical error on the part of coordinator, etc.), and the pre-bronchodilator FEV₁/FVC is less than 0.65, the patient will be considered to have COPD for the purpose of follow-up in this study.

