
9.5 Missing Data

Baseline data, except for spirometry measurements, are expected to have few or no missing values. Baseline spirometry measurements are expected to be missing for a small portion of patients due to patient refusal/inability, administration error, or spirometry measurements having insufficient quality. Data from the 12-month medical record review are expected to be missing for a small portion of patients (among those selected for follow-up) due to various problems accessing the medical record. Data from the 12-month patient survey are expected to be missing for a significant portion of patients due to patients not returning completed surveys.

Any missing data or data anomalies will be communicated to the site(s) for clarification/resolution. We will summarize the extent of missing data by intervention group. Patient demographics, other baseline characteristics, and available 12-month follow-up data will be compared between those with and without complete follow-up data, among those who were prospectively selected for follow-up, overall and by intervention group.

The primary analysis of the primary and secondary endpoints will be among those with complete follow-up (complete data for the relevant portions of both the chart review and follow-up survey).

For each Aim 3 endpoint that is collected via both medical record review and patient survey, sensitivity analyses will be conducted by imputing missing outcome data using different assumptions and applying the primary analysis method to the resulting data sets. Sensitivity analyses will include

1. Imputation of negative responses (i.e., responses indicating that the outcome has not occurred) for all missing patient survey responses, followed by analysis of all patients with medical record review data
2. Imputation of positive responses (i.e., responses indicating that the outcome has occurred) for all missing patient survey responses, followed by analysis of all patients with medical record review data; and
3. Multiple imputation of all missing outcome data using the observed outcomes and covariates, as described below, followed by analysis of all patients selected for follow-up.

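### Minor safety gap: clinicians are told of a very low FEV1 only from a post-bronchodilator test, with no fallback when only a pre-bronchodilator value exists

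*Protocol*

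**What the plan says.** Protocol 6.2 blinds participants and practitioners in both arms to research spirometry. The only stated exception is for safety: both are told if the participant's "post-bronchodilator FEV₁ is less than 30% predicted. For all other participants, they and their practitioners will be blinded to research spirometry results". SAP 7.3 repeats the trigger ("post-bronchodilator FEV₁ is less than 30% predicted") and adds no alternative.

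The plan expects that some people will lack a usable post-bronchodilator result:

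- Protocol 8.1 provides for a participant who is "unable to complete a post-bronchodilator spirometry (refusal, technical error on the part of coordinator, etc". A pre-bronchodilator FEV1/FVC below 0.65 then counts as COPD for follow-up purposes.
- Protocol 4.1 selects for 12-month follow-up a participant without a post-bronchodilator test whose pre-bronchodilator ratio is below 0.65, or whose pre-bronchodilator FEV1 "is less than 70% predicted, the participant will be considered to have abnormal spirometry for the purpose of follow-up in this study".
- Protocol 2.3.1 has a safety questionnaire given "prior to albuterol to exclude those with a previous adverse event with the medication". Protocol 8.4.4 also names "others at high risk due to cardiac abnormalities".
- SAP 9.5 says: "Baseline spirometry measurements are expected to be missing for a small portion of patients due to patient refusal/inability, administration error". It also lists insufficient test quality as a cause.

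SAP 7.6 says that FEV1 "values less than 30% of the predicted values will be adjudicated by the study chair". This is not limited to post-bronchodilator tests, and no step after adjudication is given.

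**The concern.** The notification is the only stated safety route through the spirometry blind, and it depends on a test that some participants will not have. Someone with very severe impairment by the plan's own 30% threshold, measured only before bronchodilator, falls among those whose results coordinators are asked to conceal. The study would then hold a seriously abnormal value that neither the participant nor the clinician sees.

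Other routes soften this:

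- Clinicians treat on their own judgment (Protocol 6.4).
- PEF is measured in everyone (Protocol 8.1). A low PEF with a CAPTURE score of 2 to 4, or any score of 5 or more, makes the participant CAPTURE+.

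However, the CAPTURE result goes only to intervention practices. Control practitioners are blinded to both the questionnaire and PEF, and a score of 0 or 1 is CAPTURE- whatever the PEF. What is at stake is a missed or late warning for very few people, mainly in control practices.

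**Working it through.** **Rules compared.** Each pre-/post-bronchodilator rule is set out below, with what happens when the post-bronchodilator test is missing.

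| Purpose | Post-bronchodilator rule | Fallback on pre-bronchodilator value | Where |
|---|---|---|---|
| COPD status for follow-up | FEV1/FVC < 0.70 | FEV1/FVC < 0.65 | Protocol 8.1; SAP 7.6 |
| Selection for 12-month follow-up | FEV1/FVC < 0.70 or FEV1 < 80% predicted | FEV1/FVC < 0.65 or FEV1 < 70% predicted | Protocol 4.1; SAP 6.1 |
| Safety notification | FEV1 < 30% predicted | none | Protocol 6.2; SAP 7.3 |

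**Who is caught.** A pre-bronchodilator FEV1 of 25% predicted is below 80%, so a post-bronchodilator test is due. If it is refused, fails technically, is withheld for safety or is of unusable quality, the trigger cannot be met and the results stay blinded. A participant who used an inhaler in the two hours before testing is not affected, because that single test counts as post-bronchodilator (Protocol 8.1). Someone whose pre-bronchodilator test is also unusable is not affected either, since there is no value to report.

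**How many.** The plan gives no figure to reproduce, so this is an order-of-magnitude estimate.

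1. Spirometric COPD cases. SAP 13.1 reports roughly 2 per practice (interim, March 2020): 2 × 100 practices = 200.
2. Cross-check from SAP Table 6. Patients: 663 + 750 + 431 + 280 + 468 + 446 = 3038. Practices: 15 + 15 + 9 + 6 + 11 + 12 = 68. Then 3038 / 68 = 44.7 per practice; 2 / 44.7 = 4.5%; applied to 5000 patients, 224.
3. FEV1 below 50% predicted. Protocol 2.2 cites 10% of undiagnosed obstruction in another cohort, applied here as an assumption: 200 × 0.10 = 20 to 224 × 0.10 = 22.4.
4. No usable post-bronchodilator test after a usable pre-bronchodilator test, assumed 1% to 5%: 20 × 0.01 = 0.2 to 22.4 × 0.05 = 1.12.
5. Share of those below 30%, assumed 10% to 50%: 0.2 × 0.10 = 0.02 to 1.12 × 0.50 = 0.56.
6. Control half under 1:1 allocation: 0.01 to 0.28.
7. If missing tests were three times as common in severe disease (assumption): 0.06 to 1.68 in the whole trial.

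People without obstruction are not counted.

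**How old the values are.** Protocol version 8.0 is dated 17 July 2023.

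- A baseline visit on 19 March 2019, the cut-off in SAP 9.4, was 4.3 years old by then. Earlier visits were older.
- SAP 9.5 says that, on 21 March 2023, sites with about 84% of the patients selected for follow-up had all follow-up data. The earliest 12-month contact is day 335 (365 − 30). The latest baseline at those sites is therefore about 20 April 2022, which is 453 days or 14.9 months before version 8.0.

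**The case against.** The strongest counter-argument is SAP 7.6. Outside the notification rule, 30% is used nowhere else in the plan. It is natural to read the study chair's adjudication as leading to the safety exception, so the example case would at least reach a senior clinician. This carries weight as mitigation. But the text names no action after adjudication, and Protocol 6.2 expressly keeps everyone outside the post-bronchodilator trigger blinded.

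A post-bronchodilator trigger is also defensible in itself. Asthma is not an exclusion, so a low pre-bronchodilator value may be reversible, and the existing fallbacks serve follow-up rather than disclosure. This is a reason to require test quality and confirmation before notifying, not a reason to have no route at all.

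Two of the ways to lose a post-bronchodilator test are weakly documented. The cardiac-risk wording in Protocol 8.4.4 may be left over, since the amendment 2.0 entry for section 2.3.1 gives a rationale for no longer needing it there. SAP 9.5 speaks of missing spirometry in general. Neither is needed: refusal and technical error are in the current text, and the rationale logged for amendment 2.0 says that incomplete or refused post-bronchodilator tests had already occurred.

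Finally, spirometry procedures are detailed in a manual of procedures and a Spirometry Core operation manual that are not available here. Either might hold a notification rule. That limitation stands, and it is why confidence is medium.

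**Conclusion.** The gap is real in the written rule and minor in size. Followed literally, the plan withholds a usable pre-bronchodilator FEV1 below 30% predicted when no usable post-bronchodilator test exists. The estimate of under one person expected, or up to about 1.7 with tripled missingness in severe disease, depends on two assumed rates, a severity share borrowed from another cohort and an interim prevalence. It shows only that the number is very small. No effect on the primary analysis or on power is claimed. The point merits action because it concerns participant safety and is cheap to settle, and it falls away if the unseen manuals already cover the case.

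**What to change.** **Protocol 6.2 and SAP 7.3.** Add one clause: *If no usable post-bronchodilator test exists, the participant and clinician will also be notified when a pre-bronchodilator FEV1 of quality A to D is below 30% predicted and the study chair confirms it.* The quality range is the plan's own definition of usable spirometry (SAP 10.4).

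**SAP 7.6.** Add one sentence saying that a value confirmed by the study chair leads to this notification.

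**Existing data.** Query the baseline records once for participants who meet the new clause. Any late notice should give the test date and advise repeat clinical spirometry, because the value may be about one to four years old. If the query finds nobody, nothing further is needed for past visits. If a manual already contains the rule, cite it in Protocol 6.2.

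**Cost.** The change needs one clause, one sentence, one query and a protocol amendment with IRB approval before use. It may produce very few extra unblindings, under the same rule in both arms. Some of those notified might have exceeded 30% after albuterol. At the sites that already had all follow-up data, notification can no longer alter 12-month outcomes, so the query is the most useful part now.
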